## PROTOCOL SYNOPSIS

Protocol Number	V07
Protocol Title	Control-IQ Observational (CLIO) US Post-Approval Study
Device	t:slim X2 insulin pump with Control-IQ technology (Control-IQ System)
Type of Protocol	Post Approval Study
Rational	
This post-approval study is primarily designed to collect safety data on this US FDA-cleared product. Several secondary endpoints assessing the effectiveness of this product in real-world use will also be collected. The t:slim X2 insulin pump with Control-IQ technology will be used as intended and in accordance with FDA-approved labeling.

Objectives	
Primary objective: To demonstrate, in a real-world setting, the safety of the Control-IQ System for the management of type 1 diabetes by assessing the rate of severe hypoglycemia (SH) and diabetic ketoacidosis (DKA).
 
Secondary objective: To demonstrate, in a real-world setting, the effectiveness of the Control-IQ System for the management of type 1 diabetes by assessing the impact on patients' glycemic outcomes and user experience in the real world, during the first 12 months of use.

Primary Endpoints	
Safety Endpoints:
 
 
1) The incidence rates of severe hypoglycemia (SH) and diabetic ketoacidosis (DKA), and
 
2) The safety of the automatic population of CGM readings into the bolus calculator of the Control-IQ System
 
 
Secondary Endpoints:
 
 
3) To determine glycemic outcomes as a measure of efficacy of the Control-IQ System, and
 
4) To demonstrate patient-reported satisfaction with and trust in the Control-IQ System, usability of the system, and sleep quality.
 

Duration of Study	All enrolled subjects will be monitored for outcome data for 12 months after starting the Control-IQ System.
Study Design	This post-approval study is a single-arm, prospective study. It is designed to assess 12-month safety in a real-world setting, and to support the continued assessment of the Control-IQ System for the treatment of type 1 diabetes in the United States. In addition, data will be collected to assess glycemic outcomes and user experience.

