Periodic Data Collection procedures	
100% of calls to Tandem Customer Technical Support will be screened for reportable AEs based on the definitions of SH and DKA included in this protocol. Outreach surveys will be deployed to all study participants: Monthly to collect AE incidence, and at 3, 6 and 12 months to collect other PROs (See Table 1).

Management of Adverse Events	
Safety information will be collected on an ongoing basis throughout the study as Tandem becomes aware of device-related AEs. These events will be recorded electronically from both inbound reports from customers and assessed through outreach to patients. The event, date of onset, severity, seriousness, duration and relationship to the device will be documented. All reported device-related AEs will be followed until they are adequately resolved or stabilized, until study completion/termination, or until number of outreach attempts made by clinical personnel corresponds with company's Customer Technical Support policy for adverse and device issue event outreach, whichever comes first. Safety events will be summarized based on FDA codes.

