Statistical Analysis	
Descriptive statistics will be used to evaluate outcomes vs. a comparator group. The Comparator Group will be determined using evidence from a systematic literature review examining MDI, insulin pump and sensor augmented pump (SAP) use in patients with type 1 diabetes. Primary endpoints, the risk of AE (DKA, SH), represented as risk ratio per 100 patient years, will be compared using a single sample two-tailed exact binomial test (alpha=0.05) to the expected values as extracted in the literature review. Effect size will be defined as the absolute difference in risk ratios. The safety of automatically populating CGM readings into the bolus calculator will be analyzed by correlating reported AEs, calculator usage data and CGM readings to understand if the bolus calculator may have caused the AE. This analysis will isolate AEs where three consecutive CGM readings <math>\leq 54</math> mg/dL, or <math>\geq 250</math> mg/dL existed within five hours after a correction bolus was given using an automatically populated CGM reading. Boluses using automatically populated CGM values <math>\geq 250</math> mg/dL will be analyzed and evaluated separately from boluses given for lower glucose values.
 
Secondary endpoints will be calculated as means/medians as appropriate based on data extracted from the Tandem t:connect web application and patient reported outcomes. Sensor-glucose concentrations will be analyzed per recent international consensus guidelines, to include time in target range 70-180 mg/dL, time <math>> 180</math> mg/dL, time <math>> 250</math> mg/dL, time <math>< 70</math> mg/dL, time <math>< 54</math> mg/dL.
 
Outcomes will be analyzed quarterly and tabulated using standard statistical tools such as R and Python.

----------------------	--

The study will be conducted and documented in accordance with the US Federal and Local requirements for post-market human clinical studies, the protocol, and the stipulations of the clinical trial agreement.

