#### **Severe Hypoglycemia:**

Hypoglycemia not associated with an ADE is only reportable as an adverse event when the assistance of another person was required in order to actively administer carbohydrate, glucagon, or other resuscitative actions due to altered consciousness. This means that the subject was impaired cognitively to the point that he/she was unable to treat him/herself, was unable to verbalize his/her needs, was incoherent, disoriented and/or combative, or experienced seizure or coma. These episodes may be associated with sufficient neuroglycopenia to induce seizure or coma. If glucose measurements are not available during such an event, neurological recovery attributable to the restoration of glucose to normal is considered sufficient evidence that the event was induced by a low glucose concentration.

Subjects will be instructed on this specific definition of severe hypoglycemia each time information is requested related to this AE.

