## **Primary Outcome**

Incidence rate/100 patient years for both severe hypoglycemia (SH) and diabetic ketoacidosis (DKA).

**Success Criteria/Goal:** Study participants will not experience a higher incidence of SH or DKA than incidence rates reported in the literature from analyses of similar populations. Overall outcomes will be compared to data below, derived from a recently published study using a large Type 1 Diabetes Exchange cohort (Foster et al., 2019). This study used a similar design as our postmarket study proposed here, the subjects represent our intended use population, and the event rates reported in the Foster study fall within the broader rates found in the extensive body of literature reviewed.

SH Incidence Rates (all ages)		SH Incidence Rates in Children			SH Incidence Rates in Adults	
All ages (13-93)			Ages 6-12	Ages 13-17	Ages 18-93	
All insulin delivery	25/100 PY	All insulin delivery	22/100 PY	20/100 PY	All insulin delivery	30/100 PY
MDI	37/100 PY	MDI	28/100 PY	34/100 PY	MDI	38/100 PY
IPT	23/100 PY	IPT	16/100 PY	13/100 PY	IPT	27/100 PY
DKA Incidence Rates (all ages)		DKA Incidence Rates in Children			DKA Incidence Rates in Adults	
All ages (13-93)			Ages 6-12	Ages 13-17	Ages 18-93	
All insulin delivery	11/100 PY	All insulin delivery	13/100 PY	14/100 PY	All insulin delivery	9/100 PY
MDI	17/100 PY	MDI	22/100 PY	25/100 PY	MDI	13/100 PY
IPT	7/100 PY	IPT	5/100 PY	9/100 PY	IPT	7/100 PY

The full literature review can be found in Attachment 1 of this protocol.

The safety of automatically populating CGM readings into the bolus calculator will be analyzed by correlating reported AEs, calculator usage data and CGM readings to understand if the bolus calculator may have caused the AE. This analysis will isolate AEs where three consecutive CGM readings  $\leq 54$  mg/dL, or  $\geq 250$  mg/dL existed within five hours of receiving a correction bolus using an automatically populated CGM reading. All CGM readings within 5 hours after the bolus is given will be evaluated. In addition, correction boluses using automatically populated CGM values  $\geq 250$  mg/dL will be analyzed and evaluated separately from boluses given for lower glucose values.

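### The bolus-calculator safety analysis selects adverse events by the same CGM trace that supplied the dosing value, so a severe hypoglycemia or DKA event with a persistently biased or interrupted trace can drop out

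*Combined protocol and SAP*

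**What the plan says.** The protocol synopsis lists as its second primary safety endpoint "The safety of the automatic population of CGM readings into the bolus calculator of the Control-IQ System", and Study Objectives repeats it as a primary objective. (The Study Endpoints section names only the SH/DKA rate.) Under Primary Outcome the method is described as "correlating reported AEs, calculator usage data and CGM readings to understand if the bolus calculator may have caused the AE".

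The selection rule follows: "This analysis will isolate AEs where three consecutive CGM readings" at or below 54 mg/dL, or at or above 250 mg/dL, "existed within five hours of receiving a correction bolus using an automatically populated CGM reading". The text adds: "All CGM readings within 5 hours after the bolus is given will be evaluated". The Statistical Analysis entry of the synopsis gives the same rule ("existed within five hours after a correction bolus was given using an automatically populated CGM reading"). Correction boluses based on auto-populated values of 250 mg/dL or more are to be looked at separately. Neither place names a meter or laboratory glucose, and neither says how a bolus is tied to the onset of the adverse event.

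The events themselves are defined clinically. For SH: "If glucose measurements are not available during such an event, neurological recovery attributable to the restoration of glucose to normal is considered sufficient evidence". DKA rests on symptoms, treatment in a facility and a reported diagnosis, with no CGM criterion.

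On timing, the synopsis says: "The event, date of onset, severity, seriousness, duration and relationship to the device will be documented". The form contents listed under Adverse Event Definitions include dates of onset and resolution and no clock time, though further detail may be recorded.

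**The concern.** The question is whether feeding a CGM value straight into the bolus calculator contributes to harm. One way it could is that the value is wrong. If the sensor then stays wrong, the trace used to select events carries the same error. A falsely high sensor can support a larger correction and afterwards fail to show the low that followed. A sensor that drops out after the bolus may leave no run of three readings. Either way, an event that counts fully in the SH/DKA rate is not isolated for the calculator analysis. A low count from this analysis would then partly reflect the selection rule, and would be least informative about persistent sensor error.

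A second, separate matter is linkage. A five-hour window needs an onset time. A date leaves open which of the day's boluses came before the event.

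**Working it through.** The plan states no error rate, power, margin or event count for this endpoint, so there is no figure to reproduce. The check applies the rule to its own thresholds.

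**Inputs from the protocol:** 54 and 250 mg/dL, three consecutive readings and five hours (Primary Outcome); one reading every 5 minutes (General Description of Investigational Device). Five hours therefore hold 5 × 60 / 5 = 60 readings, and a run of three spans 10 to 15 minutes.

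**Assumptions:** true glucose values, a persistent proportional bias, and the number of qualifying boluses per day.

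**1. Over-reading that keeps a true low above 54.** Formula: 54 / true − 1.

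| True nadir (mg/dL) | Over-reading needed |
|---|---|
| 50 | 8% |
| 45 | 20% |
| 40 | 35% |
| 35 | 54% |

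Because the rule needs three readings in a row, a brief nadir can be hidden by less bias than this.

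**2. Whether the upper arm rescues the event.** Suppose 25% over-reading. A true 160 at the bolus reads 160 × 1.25 = 200, and a true nadir of 45 reads 45 × 1.25 = 56. Neither threshold is met and the SH is not isolated. The upper arm would fire only if true glucose were at least 250 / 1.25 = 200 for three readings in the window. This shows what the filter does. It does not show that a 25% error would cause SH.

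**3. Under-reading that keeps a true high below 250.** Formula: 1 − 250 / true. The results are 17% at 300, 29% at 350 and 37.5% at 400 mg/dL.

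**4. Gaps.** A gap excludes an event only if no qualifying run exists anywhere in the five hours.

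**5. Linkage with onset known only to the day.** Boluses that could lie within five hours before onset cover 24 + 5 = 29 hours instead of 5, a ratio of 29 / 5 = 5.8. With k qualifying boluses per day spread evenly, the candidates per event are k × 29/24 against k × 5/24:

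| k (assumed) | Date only | Clock time |
|---|---|---|
| 1 | 1.2 | 0.2 |
| 3 | 3.6 | 0.6 |
| 6 | 7.3 | 1.25 |

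So a date mainly produces excess and ambiguous links, including boluses given after the event.

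**The case against.** The strongest reply is that the plan first describes a wider correlation of events, calculator use and CGM data, and that isolating a subset may mean flagging it rather than discarding the rest. The wording allows that. But no analysis of the remaining events is described, and this is the only selection rule given.

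There are other safeguards. Every verified SH and DKA counts in the incidence rates. The investigator assesses device relationship for any adverse event whatever the CGM shows. Adverse device effects need an additional form, and medical records can be requested. These reduce the risk that a device-related event goes unnoticed. They are general checks, however, and none requires comparing the dosing value with a reference.

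Four stronger readings are tempting, and the documents do not support them:

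- **The analysis misses wrong readings altogether.** It does not. A transient error that recovers can still give a run at or below 54. The 250 arm is not matched to event type, so an SH with a falsely very high run also qualifies. Sensor error is also never named as the sole target of the analysis.
- **An SH accepted without a glucose value is barred.** That definition concerns the time of the event. The run may fall anywhere in the five hours after the bolus.
- **Missing clock time causes the misses.** It causes ambiguous linkage, which is a different defect.
- **About 21% of events (5/24) lose part of their window at midnight.** This needs a same-date matching rule, which appears nowhere.

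That only a date is captured is itself an inference from the listed fields. The adverse event form, the eCRF instructions and the content of Appendix C are not reproduced, and a detailed SAP is promised. A later SAP could widen the selection, but it could not recover onset times that were never collected.

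**Conclusion.** The concern holds in a limited form. Applied as written, the rule does not isolate a verified SH or DKA event whose trace is persistently biased, or interrupted, so that no qualifying run appears. The size depends on assumptions: for SH, persistent over-reading of more than 8% to 54% at true nadirs of 50 down to 35 mg/dL, with no run at or above 250 in the window. How often this happens cannot be estimated from the documents, so no count of missed events is claimed. The linkage problem is separate. If only a date is held, the candidate boluses cover 5.8 times the intended window. Neither point affects sample size, power or the SH and DKA rates. This is a cheap improvement that removes an avoidable selection effect from an analysis the synopsis ranks as primary.

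**What to change.** Amend the Statistical Analysis entry of the synopsis and the Primary Outcome text together:

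- Tabulate every verified SH and DKA event that has, before onset, a correction bolus using an auto-populated CGM reading.
- Classify each by CGM pattern after the bolus: run at or below 54, run at or above 250, neither, or missing/gap. Show discordant events, such as SH with no run at or below 54, as their own category.
- Keep the present three-reading filter as a reported subset.
- Where a meter, emergency-service or laboratory glucose was already obtained at verification, tabulate it against the time-matched CGM value.
- Confirm whether onset time is captured. If it is not, add approximate onset time for SH to the form contents listed under Adverse Event Definitions, from now on.
- Where the SH time is unknown, and for DKA (whose definition gives no clear onset hour), list the auto-populated correction boluses on the onset date and the day before, and flag the linkage as uncertain.

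The cost is wording, one form field and log review for a few more events. Recalled times will be approximate, since outreach is monthly, and events already collected may lack them. Clock time should therefore not be the sole condition for entering the analysis.

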### **General Description of Investigational Device**

The t:slim X2 insulin pump with Control-IQ technology, the hybrid closed-loop insulin delivery system from Tandem Diabetes Care, is intended for subcutaneous delivery of insulin for the management of type 1 diabetes mellitus. The system uses advanced closed-loop control algorithms to adjust insulin delivery to help keep blood glucose in a targeted range. The current Control-IQ System components include the t:slim X2 insulin pump with Control-IQ technology and the current generation of the Dexcom G6 CGM.

Future iterations of the Control-IQ System may incorporate FDA-cleared modifications to the algorithm and integration with any FDA-cleared continuous glucose monitors that meet the iCGM criteria. Subjects in this study will be allowed to update their therapy with future products from Tandem Diabetes Care, Inc., and future FDA-cleared CGMs that meet the iCGM criteria, during the study period.

The Control-IQ Technology uses data from the CGM and other inputs to:

- decrease and/or suspend insulin delivery when hypoglycemia is predicted (or occurs);
- increase insulin delivery when hyperglycemia is predicted (or occurs), and
- deliver automated correction boluses when necessary to mitigate hyperglycemia

The system used in this study is comprised of a CGM sensor and transmitter along with an insulin pump with user interface (IU) for display of system information, and a control algorithm. The sensor is inserted subcutaneously and transmits data every 5 minutes to the pump via the transmitter.

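### For adverse events linked to a bolus dosed on 250 mg/dL or more, the high-glucose criterion can be met by the glucose that prompted the bolus, so it says little about whether the bolus failed

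*Combined protocol and SAP*

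**What the plan says.** The synopsis lists the safety of auto-populating CGM readings as the second safety item under its primary endpoints. The Primary Outcome section gives the aim of the analysis as "to understand if the bolus calculator may have caused the AE".

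The rule is given in the same section. "This analysis will isolate AEs where three consecutive CGM readings" are at or below 54 mg/dL, or at or above 250 mg/dL, and these "existed within five hours of receiving a correction bolus using an automatically populated CGM reading". The Statistical Analysis row of the synopsis has the same rule with a window "within five hours after a correction bolus was given using an automatically populated CGM reading".

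The Primary Outcome section adds: "All CGM readings within 5 hours after the bolus is given will be evaluated". Correction boluses whose auto-populated value was 250 mg/dL or more "will be analyzed and evaluated separately from boluses given for lower glucose values". Neither place states a different criterion for that group.

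The General Description of Investigational Device says the sensor "transmits data every 5 minutes to the pump via the transmitter".

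**The concern.** The value that puts a bolus in the high stratum (250 mg/dL or more) is also the threshold of the high-glucose arm of the flag. The window has no delay at its start, and the rule requires neither a prior fall below 250 nor a rise from the dosing value. An AE linked to such a bolus can therefore be isolated on readings taken before the bolus could show any effect.

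What is at stake is attribution. Within this stratum, a bolus that brought glucose down over an hour and a bolus that did nothing can carry the same flag. A count of AEs meeting the high-glucose arm would then largely describe where glucose started. It would say little about whether dosing on the auto-populated value contributed to the event.

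**Working it through.** The plan states no expected flag rate, threshold or power for this analysis, so there is no figure to reproduce. The check is arithmetic on the rule itself.

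**Inputs from the documents**
- Reading interval: 5 minutes (General Description of Investigational Device).
- Window: five hours after the bolus, all readings used (Primary Outcome).
- High-glucose arm: three consecutive readings of 250 mg/dL or more.
- Unit: a reported AE linked to the bolus.

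**Step 1: how soon the flag can be met.** The window holds 300 / 5 = 60 readings. The first three post-bolus readings fall at about +5, +10 and +15 minutes, so the criterion can be complete after 3 of 60 readings.

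**Step 2: starting value needed.** Let G be the dosing value and r a steady fall in mg/dL/min. The lowest of the three readings is G − 15r, so the flag is met at once if G ≥ 250 + 15r.

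| Fall r (mg/dL/min) | G needed |
|---|---|
| 0 | 250 |
| 0.5 | 257.5 |
| 1 | 265 |
| 2 | 280 |
| 3 | 295 |

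If the auto-populated reading itself counts as the first of the three, the condition becomes G ≥ 250 + 10r: 260 at r = 1 and 270 at r = 2.

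**Step 3: how often.** This needs the distribution of dosing values and early slopes among AE-linked boluses, which the documents do not give. Assumed here: the excess of G over 250 is exponential with mean 20, 40 or 60 mg/dL, and the early slope is normal with SD 0.5 or 1 mg/dL/min. With 200,000 draws per setting, the share meeting the criterion on the first three readings alone is:

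| Mean slope (mg/dL/min) | Share, range over settings |
|---|---|
| +0.5 | 89–99% |
| 0 | 80–96% |
| −0.5 | 68–88% |
| −1 | 50–79% |
| −2 | 24–63% |

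As a hand check with a fixed fall r and mean excess m, the share is exp(−15r/m). For r = 1 this is exp(−0.75) = 47% at m = 20 and exp(−0.25) = 78% at m = 60. For r = 2 it is exp(−1.5) = 22% and exp(−0.5) = 61%. These agree with the simulated rows. All the shares are lower bounds for the full five hours, because a later run of three readings at 250 or more also counts.

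**Step 4: what the flag cannot separate.** Take two AEs, each linked to a bolus dosed at 300 mg/dL.
- Trace A falls 1 mg/dL/min. Its first three readings are 295, 290 and 285, and it reaches 250 after (300 − 250) / 1 = 50 minutes.
- Trace B stays at 300 for five hours.

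The present rule flags both. A rule needing three consecutive readings of 250 or more in hours 3 to 5 (120 / 5 = 24 readings) flags B, and does not flag A if it stays below 250 from then on.

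**Step 5: the other arm.** A starting value of 250 or more cannot produce readings of 54 or less by persistence, so the low-glucose arm keeps its meaning in this stratum.

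**The case against.** The case for leaving the rule alone has four parts.

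- **The authors already separate these boluses.** This stands in part. Separation keeps the carry-over out of the lower-glucose stratum. That the same criterion applies inside the high stratum is a reading of the text, because the plan does not say so outright. But it gives one criterion and no other. The detailed statistical analysis plan promised under Determination of Sample Size would be a natural place for a second one; the promise alone does not supply it.
- **The flag is a screen.** This stands, and it limits the severity. The plan correlates AEs, calculator use and CGM data, and the clinical investigator reviews every verified AE for causality (Adverse Event Definitions). An over-inclusive screen hides no harm.
- **Nothing is tested on it.** This also stands. The binomial test and the success criterion concern severe hypoglycemia and DKA. The Study Objectives speak of monitoring this item, and the Study Endpoints section lists only the SH/DKA composite as primary safety.
- **A stricter criterion could miss true failures.** This stands, and is why the present rule should be kept and reported.

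A reader might go further and infer that nearly all boluses dosed at 250 or more will be flagged. The documents do not support that. The rule isolates reported AEs, and under Reportable Adverse Events high glucose alone is not recorded as an AE unless it is associated with an adverse device effect, so a bolus without a reported AE is never flagged. The share is also unknown. A reader might also infer that the analysis has no discriminating power in this stratum. That is too strong, because the low-glucose arm still works.

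**Conclusion.** The concern holds in a limited form. For AEs linked to a correction bolus dosed on 250 mg/dL or more, the high-glucose arm can be met within about 15 minutes by the glucose that prompted the bolus. It therefore discriminates poorly between persistence of the starting high and a bolus that failed. This follows from the stated window, the 5-minute interval and the shared threshold of 250.

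Its frequency does not follow from the documents. The range of about 24% to 99% rests on assumed starting values and early slopes, and on AE-linked boluses resembling those assumptions. Many or most is a fair summary if glucose falls slowly at first; nearly all would need a flat or rising trace.

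The severity is moderate. The item is listed among the primary endpoints in the synopsis, but the analysis is descriptive, has no test or success threshold, and does not alter the SH and DKA comparisons.

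**What to change.** Keep the present rule as the inclusive screen for all AEs. For AEs linked to boluses whose auto-populated value was 250 mg/dL or more, add a second high-glucose criterion that the pre-bolus state cannot readily meet, and report the two side by side. One example is three consecutive readings of 250 or more in the late part of the window, such as hours 3 to 5. Base any attribution statement about the high-glucose arm in this stratum on the added criterion. Leave the low-glucose arm as it is, and show the counts by arm so that the two are not merged.

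Write the rule into the detailed statistical analysis plan before the first tabulation, or, if the quarterly tabulations have begun, apply it from the next one and say so.

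The cost is one extra analysis rule on data already extracted. The downside is that the added criterion flags fewer AEs and could miss highs that were treated or ended before the late window. Reporting the present rule alongside keeps those cases visible.
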